2.7.1.3.2 Maximal interval

The maximal interval is defined as the longest interval of treatment before 48. The duration (in days) of the maximal interval will be defined as (start date of maximal interval – start date of study drug dose). Summary statistics (n, mean, std, first quartile, median, third quartile, min and max) for the duration (in weeks) of the maximal interval will be provided.

[figure not shown]
The distribution of the maximal interval is the proportion of patients with no disease activity (Q8, Q12 and Q16).

[figure not shown]
The above analysis will be done on the FAS and only on the study eye.

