12.5.3 Durability of brolucizumab 6 mg

Summary statistics of the time (in days) of the last interval with no disease activity before or at Week 48 will be provided. If there is disease activity, the last interval will be shortened by 4 weeks down to a minimum of 4 weeks. The distribution of the last interval is the proportion of subjects with no disease activity (Q4, Q8, and Q12) up to Week 48.

Summary statistics of time (in days) of the longest interval of treatment with no disease activity before or at Week 48 will be provided. The distribution of the maximal interval is the proportion of patients with no disease activity (Q8, Q12 and Q16) up to Week 48.

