2.1.1 General definitions

[figure not shown]
Study treatment: This is a single-arm study and all patients will be treated with brolucizumab 6 mg. Three loading injections (at Screening/Baseline/Day 1, Week 4 and Week 8), followed by a Treat-to-Control (TtC) regimen phase based on disease activity from Week 8 up to Week 44/46 (according to the treatment regimen). The investigator can individualize treatment intervals depending on disease activity, to adjust patient's injection regimen.

Study treatment start and end date: Study treatment start date is defined as the first date study treatment is administered and recorded on the Treatment Administration Record (DAR) Electronic Case Report Form (eCRF) page. Similarly, study treatment end date is defined as the last date of study treatment is administered and recorded on the Study Treatment Completion eCRF page.

Generally, study Day 1 is considered as the day of inclusion of the patient. However in this study, treatment is intended to be administered on the same day or if this is not possible, within 3 days after the day of inclusion of the patient.

Study day will be calculated as ((event date – study treatment start date) + 1 day) for events that occurred on or after study treatment start date (e.g. visit, AEs). For events prior to study treatment start date (e.g. time since diagnosis), study day will be negative and calculated as (event date – study treatment start date).

Baseline and post-baseline: Baseline value refers to the value of the last non-missing measurement collected prior to administration of the first dose of study treatment (Screening or Baseline visit).

A “post-baseline” value refers to a measurement taken after the first dose of study treatment. When assessments and treatments take place on the same day, treatment must occur after completion of the efficacy assessments and pre-injection safety measures (tonometry, slit lamp

[REDACTED]). If study visit assessments and the corresponding treatment occur on separate days, a repeat safety check-up will be performed prior to treatment of the eye and results documented in the source documents. More post-baseline safety measurements will be recorded in source document; visit window will be applied to OCT and IVT visits.

Change from Baseline: The difference of measure between post-baseline and Baseline is called change from Baseline.

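### The SAP formula for the duration of the maximal interval gives the time until that interval starts, not its length; the SAP last interval also omits the protocol's disease-activity reduction without declaring it

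*SAP*

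**What the plan says.** **Maximal interval.** Protocol 12.5.3 states: "Summary statistics of time (in days) of the longest interval of treatment with no disease activity before or at Week 48 will be provided". The final SAP (2.7.1.3.2) begins: "The maximal interval is defined as the longest interval of treatment before 48". It then gives the derivation: "The duration (in days) of the maximal interval will be defined as (start date of maximal interval – start date of study drug dose". The next sentence promises summary statistics "for the duration (in weeks) of the maximal interval will be provided", so the unit changes from days to weeks. The section ends with the class distribution: "The distribution of the maximal interval is the proportion of patients with no disease activity (Q8, Q12 and Q16". The nearest defined term for the reference date is in SAP 2.1.1: "Study treatment start date is defined as the first date study treatment is administered".

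**Last interval.** Protocol 12.5.3 has an analysis rule: "If there is disease activity, the last interval will be shortened by 4 weeks down to a minimum of 4 weeks". Its classes follow: "The distribution of the last interval is the proportion of subjects with no disease activity (Q4, Q8, and Q12) up to Week 48". SAP 2.1.1 and 2.7.1.3.1 take the last interval as the investigator defined it, with no reduction, and list the classes as Q8, Q12 and Q16. SAP 2.1.1 counts intervals before Week 48; SAP 2.7.1.3.1 counts those before or at Week 48. The objectives table in SAP 1.2 still describes the last interval as one without disease activity. SAP section 4 declares no change to the protocol's analyses.

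**The concern.** A duration needs two ends, and the SAP formula uses only the start of the interval. What it returns depends on when in the study the interval began. Durability is a secondary objective and the protocol asks for these statistics. A mean or median built this way would be reported as interval length but would rise the later a patient was extended.

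For the last interval, whose distribution is a named secondary endpoint, the SAP can place a patient with activity at the final assessment one class longer than the protocol rule does. A reader of SAP section 4 would not know that anything had changed.

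**Working it through.** The documents give no numerical figure for the durability endpoints, so there is none to reproduce. The check applies the two definitions to the schedules that the regimen allows.

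**Inputs.** Injections at Day 1 and Weeks 4, 8 and 16. After Week 8, intervals of 8, 12 or 16 weeks, changed by 4 weeks at a time (Protocol 6.7.2.2). Last injection by Week 46. Regular visits only: no inspection-visit injections and no visit-window shifts.

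**Formulas.**
- SAP value = (start week of longest interval − 0) × 7 days, counting from the first injection.
- Length = (end week − start week) × 7 days.
- If the SAP's reference date is instead the injection that opens the interval, the SAP value is start − start = 0 for every patient.

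**Schedules.** From Week 16 these rules give 8 distinct injection sequences. In five, the longest interval is not followed by a shorter one; no activity at its end is assumed.

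| Injection weeks from Week 8 | Longest interval starts at Week | SAP value (days) | Length (days) | Ratio, earliest tie |
|---|---|---|---|---|
| 8-16-24-32-40 | 8, 16, 24 or 32 | 56, 112, 168 or 224 | 8 × 7 = 56 | 56/56 = 1.00 |
| 8-16-28-40 | 16 or 28 | 112 or 196 | 12 × 7 = 84 | 112/84 = 1.33 |
| 8-16-24-36 | 24 | 168 | 84 | 168/84 = 2.00 |
| 8-16-24-32-44 | 32 | 224 | 84 | 224/84 = 2.67 |
| 8-16-28-44 | 28 | 196 | 16 × 7 = 112 | 196/112 = 1.75 |

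The formula equals the length only for Q8 throughout, and only if the earliest of the tied intervals is taken; the SAP does not say which to take. The fourth row (Q12, 224 days) ranks above the fifth (Q16, 196 days).

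In the other three sequences the 12-week interval is followed by a shortening, which under Protocol 6.7.2.2 is read as activity at its end. The SAP's defining sentence does not require absence of activity. It therefore selects the 12-week interval and returns 24 × 7 = 168 days (8-16-24-36-44) and 16 × 7 = 112 days (8-16-28-36 and 8-16-28-36-44). The longest other interval closed by an injection is 56 days in each.

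**Last interval.** Applying the protocol rule to assigned intervals of 8, 12 and 16 weeks:
- no activity: 8, 12, 16;
- activity: 8 − 4 = 4, 12 − 4 = 8, 16 − 4 = 12.

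The possible classes are Q4, Q8, Q12 and Q16. The protocol's list lacks Q16 and the SAP's lacks Q4, so each has three of the four. The protocol's Q4 class and 4-week floor also do not fit its own statement in 6.7.2.2 that intervals after Week 8 are 8, 12 or 16 weeks.

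Example: injections at Weeks 16, 28 and 40, Q12 kept at Week 40, activity found at Week 48. The SAP reports Q12; the protocol rule gives 12 − 4 = 8 weeks, Q8. Protocol 6.7.2.2 has disease activity assessed at Week 48/EOS with no injection given, so no later assigned interval would pick this up.

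**The case against.** This is a single-arm study and the statistics are descriptive. The named endpoint for the maximal interval is its class distribution, which can be derived without the formula. The slip is easy to see, the SAP computes another duration as end minus start plus one (2.7.1.2.5), and the programming specifications, which are not in the public text, may already be right. This limits the damage, but the formula is the only written definition of a statistic the protocol asks for, and nothing visible corrects it.

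The SAP's distribution sentence and its objectives table do carry the no-activity condition, so the omission from the defining sentence need not alter the classes. That is accepted.

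On the last interval, an investigator-defined interval may mean the one assigned after the activity assessment, so earlier activity is already reflected. This stands and narrows the effect to activity at the last assessment. The SAP introduces its class list as an example, and Q8/Q12/Q16 fits the 8/12/16-week regimen better than the protocol's own list does. That is also fair: the inconsistency lies partly in the protocol, which is why the passages need reconciling and not the SAP alone.

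The schedules are illustrations and carry no frequencies. Some figures in SAP 2.7.1.3.2 and part of the SAP's change history are not visible, so an explanation there cannot be excluded. Section 4, where a departure belongs, declares none.

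**Conclusion.** Both parts hold, and the SAP should be corrected.

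The duration formula is wrong as written: no reading of it yields an interval length. Among patients whose longest interval is Q12 it can return 112, 168, 196 or 224 days for a true 84, and for a Q16 patient 196 for a true 112. The error is confined to the descriptive duration statistics in the final analysis. The primary endpoint is unaffected, and the interim SAP marks durability as not applicable.

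The last-interval departure is undeclared and moves a patient by at most one class (4 weeks). On the assigned-interval reading, only patients with activity at the last assessment are affected. The two SAP cut-offs matter because they decide whether the Week 48 assessment can count.

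The figures rest on regular visits and on no activity at the end of the longest interval where stated. The documents do not give the number of patients in any of these groups.

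**What to change.** **Maximal interval.** Define the duration as end date minus start date of the longest treatment interval with no disease activity at its end, in one unit throughout. Tied intervals then give the same length. State whether an interval still open at Week 48/EOS counts, and how patients with no qualifying interval are reported.

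**Last interval.** Take the interval assigned by the investigator and apply the protocol's 4-week analysis reduction once if activity is present at the last assessment up to and including Week 48/EOS. Specify that activity which already led to a shortening is not deducted again; this clarification is not in the protocol. Alternatively, keep the SAP definition and record the departure in SAP section 4. Use one cut-off wording in SAP 2.1.1 and 2.7.1.3.1.

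**Categories.** Reconcile the two class lists with each other and with the 8/12/16-week regimen, so that every class the chosen derivation can produce has a place.

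**Cost.** SAP wording and two derivations to re-program; no new data. Reported durations become shorter for patients extended beyond Q8. The formula correction does not change the class distribution of the maximal interval.

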2.7.1.4 Function outcomes (Best Corrected Visual Acuity (BCVA))

Summary statistics (n, mean, std, median, min and max) of BCVA for nAMD patients will be presented along with change from Baseline in BCVA by visit along with first anti-VEGF Treatment BCVA.

The above analysis will be done on the FAS and only on the study eye.

2.9 Safety analyses

Safety measurements include duration of exposure, vital signs, and adverse events (AEs). All safety endpoints will be summarized using the Safety Set. Patients will be analyzed according to the treatment received. No imputation will be carried out for missing data.

2.9.1 Adverse events

All information obtained on AEs will be displayed by patient Summary tables for AEs will summarize only on-treatment events, with a start date during the on-treatment period ([see Section 2.1.1](#)) for definition of on-treatment period).

The count of treatment-emergent AEs, number (and percentage) of patients with treatment-emergent AEs (defined as events started after the first dose of study treatment or events present prior to start of study treatment but increased in severity based on PT) will be summarized in the following ways:

- By primary SOC and PT.
- By primary SOC, PT and maximum severity.

Separate summaries will be provided for study treatment related AEs, study procedure related AEs, need of USM, death, SAEs, other significant AEs action taken leading to study treatment withdrawn and AEs leading to dose interval adjustment (interval increase, interval reduce).

Adverse events will be summarized by presenting, the number and percentage of patients having any AE, having an AE in each primary SOC and having each individual AE (PT). Summaries will also be presented for AEs by severity. Summaries for AE will be presented for study treatment and procedure related to AEs. If a patient reported more than one AE with the same PT, the AE with the greatest severity will be presented. SOC will be presented in alphabetical order, preferred terms will be sorted within SOC in descending frequency of AEs. If a patients reported more than one AE within the same primary SOC, the patient will be counted only once with the greatest severity at the SOC level, where applicable. The AE will be presented in separate sections of ocular and non-ocular. For ocular then it will be presented by study eye, fellow eye, and any eye.

For the legal requirements of ClinicalTrials.gov and EudraCT, 2 required tables on treatment emergent AEs which are not SAEs with an incidence greater than 5% and on treatment emergent SAEs and SAEs suspected to be related to study treatment will be provided by system organ class and PT on the safety set population.

If for a same patient, several consecutive AEs (irrespective of study treatment causality, seriousness and severity) occurred with the same system organ class and PT:

- A single occurrence will be counted if there is ≤ 1 day gap between the end date of the preceding AE and the start date of the consecutive AE.
- More than one occurrence will be counted if there is > 1 day gap between the end date of the preceding AE and the start date of the consecutive AE.

For occurrence, the presence of at least one SAE / SAE suspected to be related to study treatment / non SAE has to be checked in a block e.g., among AE's in a ≤ 1 day gap block, if at least one SAE is occurring, then one occurrence is calculated for that SAE.

The number of deaths resulting from SAEs suspected to be related to study treatment, procedure and SAEs irrespective of study treatment relationship will be provided by SOC and PT.

In addition, all treatment emergent AEs and SAE will also be listed.

The by-patients listing will include: SOC/PT/Verbatim term, start date, end date, severity, USM, relationship to study treatment and procedures, whether or not it is a SAE, action taken with study treatment and outcome; duration will be calculated as (end date – start date + 1) and for ongoing AE (last visit date – start date + 1) by ocular and non-ocular. For ocular then it will be presented by study eye, fellow eye and any eye.

A summary of action taken with number and percentage of patients will presented with treatment interrupted, treatment withdrawn, not applicable and unknown.

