(1) To provide clarification and guidance on the early discontinuation of study treatment that is required for those subjects who are currently on q4w dosing beyond the first 3 monthly loading doses (“loading phase”) or would need q4w dosing beyond the “loading phase” based on the investigator’s assessment. This is as per the urgent safety measure dated 27-May-2021 based on CTH258AUS04 (MERLIN) Year 1 first interpretable results (FIR) indicating a higher frequency of IOI including Retinal Vasculitis (RV), and Retinal Vascular Occlusion (RO) in brolucizumab 6 mg q4w when compared to aflibercept 2 mg q4w (IOI: 9.3% vs 4.5% of which RV: 0.8% vs 0.0%; RO: 2.0% vs 0.0%, respectively).

(2) Additionally, as per the Urgent Safety Measure dated 10-August-2021, the results of the mechanistic study BASICHR0049 identified a causal link with an immune-mediated mechanism of the previously identified risk of Retinal vasculitis (RV), and/or Retinal vascular occlusion (RO), typically in the presence of IOI. The protocol is hence amended to require discontinuation of study treatment in subjects who develop these events.

(3) The safety sections were updated throughout the protocol including updating the Risks and Benefits section and creating a new section under Safety Monitoring to consolidate all the information regarding the risk mitigation into one section in the protocol. Additionally, as subjects treated with brolucizumab who experience intraocular inflammation may be at risk of developing retinal vasculitis and/or retinal vascular occlusion they should be closely monitored and the investigator needs to evaluate the appropriateness of continuing further with study treatment when IOI only (without RV and/or RO) is present.

(4) Finally, clarification is provided on record of prior Intraocular or periocular use of corticosteroids in the study eye and remove of the study timelines and number of sites

Changes to the protocol

Changes to specific sections of the protocol are shown in the track changes version of the protocol using strike through red font for deletions and red underlined for insertions.

Editorial changes and spelling corrections are done throughout the protocol.

Protocol sections changed in relation to urgent safety measures (USM) are:

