4.2 Rationale for dose/regimen and duration of treatment

The dose and regimen for brolucizumab is based on the following considerations:

- Brolucizumab is well tolerated at a dose of 6 mg administered 3 times every 4 weeks during the loading phase, based on the previous pivotal registration clinical Phase 3 program in which 1088 patients with nAMD received brolucizumab (RTH258-C001, RTH258-C002). The nAMD study results regarding Q12/Q8 maintenance dosing interval support stretching the interval between injections during the Treat-to-Control Phase to reduce the treatment burden (see [Section 1.1](#)).
- CRTH258AUS04 (MERLIN) is a two-year, multicenter, randomized, double masked, Phase IIIa study evaluating brolucizumab 6 mg q4w versus aflibercept 2 mg q4w in patients with nAMD with persistent fluid. Review of the 52-week FIR led to an urgent safety communication based on an increased incidence of intraocular inflammation (IOI) and related adverse events including retinal vasculitis (RV), and retinal vascular occlusion (RO) in patients with q4w dosing with brolucizumab beyond the “loading phase”. IOI including RV, and RO were reported at a higher frequency in brolucizumab 6 mg q4w when compared to aflibercept 2 mg q4w (IOI: 9.3% vs 4.5% of which RV: 0.8% vs 0.0%; RO: 2.0% vs 0.0%,

respectively). Accordingly, the CRTH258AFR03 protocol is being amended to discontinue subjects from study treatment who require treatment every 4 weeks.

- In line with current clinical practice, ophthalmology association recommendations, and labels of approved anti-VEGF drugs in most countries worldwide, the treatment frequency can be adjusted based on the Investigator's assessment of disease activity.
- Current evidence from large ranibizumab studies in nAMD (CRF002A2411 - TREND, CRF002ACA06 - CAN-TREAT, CRF002AAU15 - FLUID, CRF002AAU17 - RIVAL) indicates that the Treat-and-Extend regimen is efficient and clinically comparable to monthly injections in improving visual acuity while reducing the number of visits and treatments (see [Section 1.1](#)).
- In this SWIFT study, patients will be suboptimal anatomically controlled (active CNV with residual IRF and/or SRF) despite a Q4 to Q8 anti-VEGF treatment. For these non/partially responder patients, the treatment should be as frequent as needed. That is why a Q8 treatment will be allowed since Week 8 and the interval extension will be optional after the loading phase.

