6.7.2.2 Treat-to-Control Phase

After the Initiation Phase, the Treat-to-Control Phase will start from Week 8, where the injection interval will be extended by 4 weeks to Week 16 (according to disease activity).

The Treat-to-Control Phase rules are defined as follows:

- Following Week 8, treatment intervals will be either 8 weeks, 12 weeks, or 16 weeks. A patient must be discontinued from further study treatment if treatment is required more frequently, i.e., every 4 weeks.
- The assessment of disease activity will be performed at each visit by the Investigator.
- At Week 8, based on Investigator's judgment of visual and/or anatomic outcomes, treatment intervals will be extended by 4 weeks at a time, if there is no disease activity, i.e. no change in visual acuity and in other signs of the disease (e.g. IRF, SRF, hemorrhage, leakage, etc.). From Week 16, the injection interval can be maintained on Q8 (or Q12 from Week 28) if the Investigator deems that the patient will not benefit from treatment interval extension, with a minimal interval of 8 weeks.
- If disease activity recurs, treatment intervals should be shortened accordingly by 4 weeks at a time or to a minimal interval of 8 weeks.
- At the Investigator's discretion, an inspection visits at Week 14, i.e. 6 weeks after the 3rd injection, can be performed. If there is no disease activity in the study eye at Week 14, as assessed by the Investigator, the study treatment will not be administered; the next visit and injection will take place at Week 16. If disease activity is observed by the Investigator in the study eye at Week 14, the study treatment will be administered by the Investigator, and the subject will be discontinued from further study treatment.
- Inspection visits 10 weeks after the last injection can be performed at the Investigator's discretion when the injection interval is extended from 8 weeks to 12 weeks. If there is no disease activity in the study eye at the inspection visit as assessed by the Investigator, the study treatment will not be administered; the next visit and injection will take place 2 weeks later, i.e. 12 weeks after the previous study treatment. If disease activity is observed by the Investigator in the study eye at the inspection visit, the study treatment will be administered by the Investigator; the injection interval will be reduced to 8 weeks and the next injection visit will be 8 weeks after the inspection visit.

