1.1 Study design

This is a prospective, single-arm, open-label, multicenter study to evaluate the efficacy and safety of brolucizumab 6 mg in pretreated suboptimal anatomically controlled patients with nAMD.

Approximately 295 adult patients will be screened and included (10% dropout rate expected) in France.

Before inclusion in the study, a patient must have a washout period of 4 weeks to 8 weeks (from 26 to 62 days inclusive) *versus* his/her last administration of a licensed anti-VEGF drug (i.e. Lucentis®, Eylea®).

The maximum study duration for 1 patient is 48 to 50 weeks, according to the patient schedule.

[figure not shown]
The study will consist of 2 periods ([Figure 1-1](#)):

- Open-label Treatment Period (from Screening/Baseline (Day 1) to Week 44 or Week 46 according to patient schedule)
- Follow-up Period (from Week 44 to Week 48 or from Week 46 to Week 50 according to patient schedule)

According to the patient treatment schedule, the last treatment can be at Week 44 or Week 46. If the last treatment visit is at Week 46, the End-of-study visit will be at Week 50 (at least 4 weeks after the last injection) instead of at Week 48.

Patients will require attending 5 mandatory study visits: Screening/Baseline (Day 1), Weeks 4, 8, 16, and 48/50. The other visit time points will depend on the injection regimen of the patient.

Figure 1-1 Study design

a End of treatment: Week 38/40/42/44/46 according to treatment schedule.

b End of study: at least 4 weeks after the end of treatment. For patients receiving the last IVT at Week 46, the EOS Visit will be at Week 50, 4 weeks following their last treatment.

The fellow eye will be treated at the discretion of the Investigator.

The Screening Visit and the Baseline Visit are the same visit in this study. Patients will receive 3 initial doses every 4 weeks (Day 1, Week 4 and Week 8). From Week 8, based on Investigator's judgment of visual and/or anatomic outcomes, the injection interval can be maintained on Q4 regimen or extended by 4 weeks at a time if there is no disease activity, as per Investigators decision, e.g. no change in visual acuity and in other signs of the disease (e.g. IRF, SRF, hemorrhage, leakage, etc.). If disease activity recurs, the injection interval should be shortened accordingly by 4 weeks at a time or to a minimal interval of 4 weeks.

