2.3 Analysis sets

The Enrolled Set (ENR) includes all patients who signed an ICF and are assigned patient numbers.

The Safety Set (SAF) includes all patients who received at least one IVT injection of study treatment.

The Full Analysis Set (FAS) will be the same as the Safety Set in this study and will be used as primary population to analyze the efficacy endpoints.

Urgent Safety Measure Set (USM): If any subject needs Q4 treatment interval at any time point after initial loading phase then that subject qualify for USM.

The Per-Protocol Set (PPS) is a subset of patients in the FAS without PDs with impact. The list of PD criteria will be provided in edit checks specification (ECS) document.

Full Analysis Set Estimand (FAS-EST): The FAS-EST comprises all patients who are in FAS and did not discontinue treatment in the entire study due to COVID-19.

Per-Protocol Set Estimand (PPS-EST): The PPS-EST is a subset of patients of the FAS-EST without PDs with impact due to COVID-19.

When assessing the robustness of the overall efficacy conclusions, considerations will be given to the analysis based on the estimand using FAS-EST and PPS-EST. The expectation for comparing of both estimands is to have similar conclusions. Inconsistencies in the results will be examined and discussed in the CSR.

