2.9.1.1 Adverse events of special interest / grouping of AEs

The number (%) of patients with adverse events of special interest (AESI) will be summarized by Standardized MedDRA Query and PT. A listing will also be provided.

A Case Retrieval Sheet (CRS) with the exact composition of the AE groupings is to be used to map reported AEs to the AESI groupings. This file may be updated (i.e. it is a living document) based on review of accumulating trial data, and therefore the groupings are also subject to potential change. The most up-to-date version of the CRS will be used at the time of the analysis.

The number and percentage of patients with any AESI, having an AESI in each SOC and having each individual AE (PT) will be presented by SOC and PT.

The number and percentage of patients by AESI type along with incidence rate per patient and per 1000 injections will be provided. Incidence rate per patient is defined as number of patients in AESI type/total number of patients in safety analysis set and incidence rate per 1000 injection is define as (number of occurrence of AESI type/total number of injections)*1000.

The number and type of AESI will be plotted according to the time after last brolucizumab injection and time since first brolucizumab injection.

Summary statistics for change from baseline in BCVA after end date of AESI will be provided for each AESI type and change from baseline in BCVA will be plotted overall and for each type of AESI.

Patients demographics, baseline characteristics and medical history will be provided for AESI patient with safety set.

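### The urgent-safety-measure AE summary appears to group patients by needing q4w rather than receiving it, so any interval-related excess of IOI, RV or RO could be diluted

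*SAP*

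**What the plan says.** - **Source of the interval signal.** Protocol 4.2 cites a 52-week q4w study (MERLIN): "IOI including RV, and RO were reported at a higher frequency in brolucizumab 6 mg q4w when compared to aflibercept 2 mg q4w". The IOI figures are 9.3% against 4.5%. The exposure is q4w dosing actually given beyond loading.
- **USM group.** SAP 2.3 defines it by need: "If any subject needs Q4 treatment interval at any time point after initial loading phase then that subject qualify for USM".
- **AE tables.** SAP 2.9.1 states: "Separate summaries will be provided for study treatment related AEs, study procedure related AEs, need of USM, death, SAEs". It does not say whether need of USM means the 2.3 set.
- **AESI tables.** In SAP 2.9.1.1 the rate per 1000 injections is "number of occurrence of AESI type/total number of injections)*1000", over all injections. The plots use time since the first and the last injection.
- **Other USM analysis.** The exposed/not-exposed comparison in SAP 2.6.1 covers disease activity only.
- **Patients who may have had q4w after loading.** The Amendment 3 rationale covers "subjects who are currently on q4w dosing beyond the first 3 monthly loading doses" as well as patients who would need such dosing. SAP 1.1 still says "the injection interval can be maintained on Q4 regimen or extended by 4 weeks at a time if there is no disease activity".
- **Patients who needed q4w and were stopped.** Protocol 6.7.2.2 says: "A patient must be discontinued from further study treatment if treatment is required more frequently, i.e., every 4 weeks". Sections 6.1.4 and 9.1.1 agree.

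**The concern.** The signal in Protocol 4.2 concerns injections received, while the SAP's USM group is built on need. A patient given several q4w injections before the USM and a patient stopped before any q4w injection both meet the SAP 2.3 definition. If the AE summary rests on that set, the two are reported as one.

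The interval signal caused a substantial amendment, and this trial may hold some of the relevant exposure in pretreated patients. With the planned tables, a reader of the study report could not see whether AESIs clustered after short intervals. A pooled figure close to the overall rate could be taken as reassurance that it does not provide.

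**Working it through.** The plan states no figure on this point, so there is none to reproduce. The check has three parts.

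**1. Does any planned AE or AESI output use the interval received?**

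| Output | Basis | By interval received? |
|---|---|---|
| AE summary, need of USM (2.9.1) | need, if read with 2.3 | no |
| AEs leading to interval adjustment (2.9.1) | action taken after the event | no |
| AESI per 1000 injections (2.9.1.1) | all injections | no |
| AESI plots (2.9.1.1) | time since first or last injection | no |
| Exposed/not exposed to USM (2.6.1) | disease activity | not a safety analysis |
| Exposure summaries (2.5.1) | injection counts, interval changes | not linked to AEs |

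**2. What does pooling do?** Let f be the share of the needed-q4w set that received q4w after loading, a the IOI risk in that share and r the risk in the rest. Then:

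pooled risk = f × a + (1 − f) × r, and pooled risk − r = f × (a − r).

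So the set shows the fraction f of the excess. Illustrative inputs are a = 9.3% (Protocol 4.2) and r = 3.2% or 5.3% (the male and female rates in HAWK and HARRIER, Protocol 4.5). The full excess would be 9.3 − 3.2 = 6.1 or 9.3 − 5.3 = 4.0 points. The values of f are assumed.

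| f | r = 3.2% | r = 5.3% | Excess shown (points) |
|---|---|---|---|
| 0.25 | 4.7% | 6.3% | 1.5 or 1.0 |
| 0.50 | 6.25% | 7.3% | 3.05 or 2.0 |
| 0.75 | 7.8% | 8.3% | 4.6 or 3.0 |

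Follow-up may add to this. The SAP 2.1.1 on-treatment window ends 30 days after the last injection. A last injection at Week 14 or 16 gives 14 × 7 + 30 = 128 or 16 × 7 + 30 = 142 days. A last injection at Week 44 or 46 gives 338 or 352 days. The ratio is 128/352 = 36% to 142/338 = 42%. Protocol 12.5.5.1 extends the window to end of study if that is later, which would shrink this second effect but not the pooling.

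**3. How precise would a split by interval received be?** With 2 events in 20 patients the Clopper-Pearson 95% interval is 1.2% to 31.7%; with 5 in 50 it is 3.3% to 21.8%. At a true risk of 9.3%, the chance of no event in 20 patients is (1 − 0.093)^20 = 0.14.

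**The case against.** Much of the case on the other side stands, and it limits the point.

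- **The risk is not confined to q4w.** A reader might infer that the known inflammation risk comes from q4w dosing. Protocol 1.1 and 4.5 describe IOI, RV and RO from post-marketing use, an immune-mediated causal link, and more IOI than aflibercept in the pivotal studies with Q12/Q8 maintenance. Only the added frequency in 4.2 is tied to the interval.
- **Need of USM may be an attribute of the event.** SAP 2.9.1 lists USM as a field in the AE listing and does not cite the 2.3 set. The link is inferred. Under either reading, no table uses the interval received.
- **The q4w-received group is not established.** A reader might infer that the trial certainly holds these data. The support is amendment rationale and SAP design text that conflicts with the current protocol. Recruitment was planned from January 2021 (Amendment 2), and 27 May 2021, the USM date, less 84 days is 4 March 2021. If those dates held and dosing changed on the USM date, only patients enrolled by about then could have had a Week 12 injection. No count is given.
- **The illustration is not an estimate.** The 9.3% is a 52-week rate under q4w, and patients here may have had far fewer such doses. The 3.2% and 5.3% are rates by sex in treatment-naive patients. The subtraction crosses studies.
- **Case-level review is possible.** Listings, time-from-injection plots and exposure data help, but they give no rates or denominators by interval.
- **Scope and confounding.** The safety objective is AE incidence in a single arm, and the interval follows disease activity. Any split is descriptive.

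**Conclusion.** The point holds in limited form. The only USM group defined in the SAP rests on needing q4w; the USM-related AE summary appears to use it; and no AE or AESI table is by interval received. Any interval-related excess in IOI, RV or RO would be diluted to the fraction f if three conditions are met: the summary uses the 2.3 set, the set contains both kinds of patient, and those stopped have a lower rate than those dosed q4w.

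A reader might infer from the illustration that 25 to 75% of the excess is lost. The documents do not support that: the loss is simply 1 − f for assumed f, and neither group's size is given. The size is unknown. The primary Week 16 analysis is unaffected.

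**What to change.** Analysis only, in SAP 2.9.1 and 2.9.1.1:

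1. State that need of USM refers to the set in SAP 2.3.
2. Add a descriptive AESI table by exposure received before onset. Attribute each AESI to the last injection before onset. Keep loading injections as their own class, and class each post-loading injection by its preceding interval: about 4 weeks, about 6 weeks (a Week 14 injection), 8 weeks or more. Give AESIs per 1000 injections in each class.
3. Give patient counts and percentages with Clopper-Pearson intervals for patients with any post-loading q4w injection before onset. Show patients who needed q4w but were stopped without a q4w injection as a separate row.
4. Label the table descriptive, because the interval follows disease activity.

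A simple patient split at under 8 weeks would not serve. Patients injected at Week 14 and then stopped would fall both in the short-interval group and in the needed-but-stopped row. Early IOI cases, who must stop treatment under Protocol 9.1.1, would be counted as having no short interval. Dates alone are also not enough: with ±7 days at each visit, a nominal 8-week interval can be 56 − 14 = 42 days, the same as a nominal 6 weeks. Visit and injection date should be used together.

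The cost is SAP wording, a derived flag from injection dates already recorded (Protocol 6.6.1), and one sparse table. The downside is that the q4w-received group may be small, with wide intervals.

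Separately, the SAP 1.1 text allowing a Q4 regimen and the text in Protocol 6.1.4, 6.7.2.2 and 9.1.1 stopping such patients contradict each other and must be reconciled.
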